## **Objective**

We describe the first evaluation of the VA's automated texting system (aTS). Consistent with an implementation-effectiveness hybrid 2 study design, our aims were to: (1) qualitatively and quantitatively assess implementation outcomes for the aTS; and (2) assess impact of the aTS on HCV clinical outcomes in a real-world setting.

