### ***Measures and Data Collection***

PRISM domains (implementation and sustainability infrastructure, intervention characteristics, recipients via both patient and organizational perspectives, external environment) guided the measures and data collection and are denoted in parentheses.

**Implementation Processes: Facilitation (Implementation and Sustainability Infrastructure).** The external facilitator (VY) logged facilitation events on a tracking sheet, including facilitation date, length of time, mode of delivery (i.e., email, phone call, or in-person visit), purpose, notes, and other observations. From the perspective of the primary facilitator, if multiple facilitation events occurred in one day, only one event per person, per day was counted.

**Implementation Outcomes: Texting Use (Intervention).** Providers logged the number of patients who were offered the aTS and noted whether patients enrolled or declined, including the reason for declining. The content of patient text message replies was extracted from the aTS portal. To be eligible for the texting protocol, patients had to be starting HCV medication treatment. There were four steps to initiate a patient on the aTS: (1) providers verbally offered patients the aTS, (2) providers registered interested patients in the aTS portal and assigned them the HCV protocol, and (3) once a patient was registered, the aTS would send an automated text message requesting the patient authenticate themselves by replying to this initial text message thus prompting the assigned HCV protocol to begin, and (4) patients actively text with the aTS.

**Clinical Effectiveness Outcomes.** Medication adherence was measured via patient text response rate, operationalized as the number of days of text-confirmed medication taking divided by the number of days

receiving medication reminder texts. Consistent with other adherence standards, an affirmative text response rate of  $\geq 80\%$  was considered high adherence.ix Clinical data, including HCV treatment regimen and duration, and lab dates and results, were extracted from VA's National HCV Dashboard with data from VA's Corporate Data Warehouse.x The goal of treatment is to achieve cure, or sustained virologic response (SVR), where there is an undetectable HCV lab result 12 weeks after completion of treatment.

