*Questionnaires (Recipients, intervention, implementation).* Patients at each clinic completed baseline and follow-up (after 8-12 weeks of using the aTS) questionnaires. The comparison clinics followed the same schedule, though without any use of texting. Patient questionnaires covered the topics of self-rated health status, adherence, illness perception, health engagement and activation, technology use, experiences with the aTS (usability, usefulness, working alliance), and demographics.xi,xii,xiii,xiv,xv,xvi Provider questionnaires followed the same schedule and covered topics of technology experience, quality improvement culture, climate and readiness for implementation, satisfaction with current local HCV care processes, experiences with the aTS (usability and usefulness), and demographics.xvii,xviii,xix,xx Questionnaires were pre-tested for clarity, redundancy, and relevancy by two patients and four providers and implementation scientists independent of the study team.

For effectiveness outcomes measures, we combined patients who were using the aTS regardless of whether they were in UI or AI clinics. These were referred to as “texters”. In contrast, “non-texters” could come from UI or AI clinics (patients who agreed to participate in the project but never completed the last step of authenticating themselves with the aTS, and thus never received any text messages), as well as from the two comparison clinics that did not implement the aTS.

*Semi-structured interviews (all PRISM domains).* Qualitative semi-structured telephone interviews were conducted with patients and providers who used or were invited to use the aTS. Interviews were conducted in the follow-up period during September and October 2017. The interview guides were informed by PRISM domains (denoted in parentheses) and explored issues regarding barriers to and facilitators to aTS uptake and use (intervention; implementation and sustainability), usability and usefulness of the aTS (intervention), and how the aTS was experienced by patients and providers (recipients) in the course of treatment and daily practice (external environment). Interviews were conducted by members of the study team not involved in facilitation (BP, CG) and lasted about 30 minutes.

For each questionnaire or qualitative interview completed, patients received a \$10 store gift card to compensate them for their time.

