### **Data Analysis**

Descriptive and bivariate analyses of facilitation log data were conducted to compare facilitation dose, comparing UI and AI implementation groups. Descriptive and bivariate analyses were conducted on provider and patient questionnaires, text message frequencies, and clinical data to assess differences between implementation groups (UI and AI) in implementation outcomes. We then compared clinical effectiveness outcomes between texters and non-texters. We examined patient progression through the aTS initiation process, by calculating the percent retained from one step to the next, by UI and AI implementation group. Chi-square tests were used to assess differences between the two groups. All analyses were conducted in RStudio Version 1.0.153 and statistical significance was defined as  $p < 0.05$ .xxi

Qualitative interviews were audio recorded, transcribed verbatim, and then analyzed using NVivo 11 software.xxii Thematic analysis of all qualitative data (interview transcripts, meeting notes, text messages) was conducted.xxiii PRISM domains provided the deductive *a priori* codes and other codes emerged with inductive coding. The triangulation of quantitative and qualitative data served as a final step of analysis.

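### The only stated comparison for the clinical-effectiveness aim, texters versus non-texters, is not randomised, has no stated adjustment and pools two kinds of non-texter; it supports an association, not aTS impact

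*Combined protocol and SAP*

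**What the plan says.** The Objective section sets aim 2 as to "assess impact of the aTS on HCV clinical outcomes in a real-world setting". For clinical effectiveness, the Data Analysis section states one comparison: "We then compared clinical effectiveness outcomes between texters and non-texters".

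The groups are defined under Measures and Data Collection, in the questionnaire text. Texters are aTS users from usual-implementation (UI) and augmented-implementation (AI) clinics combined. Non-texters come from two sources:

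- in UI and AI clinics, "patients who agreed to participate in the project" but who "never completed the last step of authenticating themselves with the aTS, and thus never received any text messages";
- patients of "the two comparison clinics that did not implement the aTS".

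The same section, under Texting Use, lists four steps to start a patient: a verbal offer; then "providers registered interested patients in the aTS portal and assigned them the HCV protocol"; then an automated text "requesting the patient authenticate themselves by replying to this initial text message"; and finally "4) patients actively text with the aTS". Providers also log patients who decline, with the reason.

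Setting & Participants says that seven clinics were randomised to UI or AI, and that two comparison clinics were chosen purposively for similar volume, complexity and locale. The Design section says these matched sites helped to determine effectiveness. Data Analysis names descriptive and bivariate analyses and chi-square tests.

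**The concern.** Aim 2 is worded causally, but the comparison is between users and non-users. If patients who reply to the authentication text have a different prognosis from those who do not, part of that difference would be read as an effect of the aTS, even if the aTS does nothing. Pooling the two sources of non-texter hides how far each is affected and makes the result depend on how many patients each contributes. At stake is whether a difference in sustained virologic response (SVR) or in questionnaire outcomes can be reported as impact.

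**Working it through.** The plan gives no group sizes, authentication rate, outcome rates or target difference, so there is no figure to reproduce. Most of the check is a reading of the text.

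1. **Randomisation.** Clinics were allocated to UI or AI, and both had the aTS. The UI versus AI comparisons are tied to implementation outcomes in Data Analysis. Neither gives a randomised comparison of texting with no texting.
2. **Selection within aTS clinics.** Non-texters there had agreed to take part and missed what is called the last step. The natural reading is that they had already been offered the aTS and registered, so mainly the patient's own reply separates them from texters.
3. **Selection relative to comparison clinics.** Here texters are also selected by provider offer, patient interest and registration. Comparison-clinic patients passed through none of these steps.
4. **Adjustment.** No covariate-adjusted, stratified or propensity method is stated, and no allowance for clinic. Yet self-rated health, engagement and activation, technology use and demographics are covered by the baseline questionnaire, and regimen was extracted from clinical data.
5. **Classification.** Authentication is the last step in the group definition but step 3 of 4 under Texting Use. Patients who authenticated and then did not text are not clearly placed. Decliners are placed in neither group.
6. **Adherence.** Text-response adherence divides days of text-confirmed medication taking by days receiving reminder texts. Non-texters received none, so the denominator is zero and the measure is undefined for them. This needs no assumption.

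**Illustration of points 2 and 3 (every input assumed).** Let G be the outcome gap between patients who would and would not authenticate, e the share who would, and w the share of non-texters who come from aTS clinics. Set the aTS effect to zero and give all clinics the same mix.

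- Texters minus aTS-clinic non-texters = G.
- Texters minus comparison-clinic patients = (1 − e)G.
- Texters minus pooled non-texters = [w + (1 − w)(1 − e)]G, which lies between the two.

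With e = 0.70 and G = 5 points, these are 5.0 points, 0.30 × 5 = 1.5 points and, at w = 0.5, (0.5 + 0.5 × 0.30) × 5 = 3.25 points. If G = 0 all three are zero; if G is negative the sign reverses.

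The pooled share varies widely with the assumed counts. Let N1 be the number of aTS-clinic participants and N2 the number of comparison participants, so that w = N1(1 − e)/[N1(1 − e) + N2].

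| N1 | N2 | e | w | Share of G |
|---|---|---|---|---|
| 50 | 100 | 0.90 | 5/105 = 0.048 | 14% |
| 200 | 100 | 0.75 | 50/150 = 0.333 | 50% |
| 200 | 40 | 0.50 | 100/140 = 0.714 | 86% |
| 400 | 40 | 0.50 | 200/240 = 0.833 | 92% |

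None of these rows is a bound.

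**Seven versus two clinics as an alternative.** If the shares who would authenticate are e1 in aTS clinics and e2 in comparison clinics, this contrast carries (e1 − e2)G. That is zero with the same mix, and ±20% of G if the shares differ by 0.20 either way.

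Its precision from clinic variation alone: √(1/7 + 1/2) = 0.8018. With equal between-clinic variances, t on 7 df is 2.365 and the 95% half-width is 1.896 × the between-clinic SD. Without that assumption, and with equal observed variances, the Welch df is (1/7 + 1/2)² / [(1/7)²/6 + (1/2)²/1] = 1.63, t is 5.385 and the half-width is 4.32 × SD. For an assumed SD of 2 to 5 points this gives 3.8 to 9.5 points, or 8.6 to 21.6 points.

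**The case against.** The strongest reply is that a no-aTS control was designed in: the Design section gives the matched comparison sites this role, and they were chosen for similar volume, complexity and locale. That is real mitigation between clinics. It does not remove selection between patients, because the matching was purposive and on clinic features, no separate contrast with those sites is stated, and they are merged into the non-texters.

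It is also fair that this was a quality-improvement project in routine care, where self-selected use is inherent, and that decline reasons, step retention and interviews can describe how selection arose. This justifies the design. It does not turn a user versus non-user difference into impact, and none of that information is stated to enter the comparison.

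Three stronger readings are tempting and are not supported:

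- **That an unadjusted chi-square test was specified for texters versus non-texters.** The chi-square sentence follows the analysis of step retention by UI and AI, and its two groups may be those. What can be said is that no adjusted method is stated.
- **That provider offer and registration separate texters from non-texters within aTS clinics.** The group definition suggests that both had passed those steps.
- **That the step-numbering conflict is itself a serious flaw.** Authentication may simply complete set-up, with step 4 meaning continued use. The wording needs reconciling, no more.

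**Conclusion.** The point holds as a gap in the plan. The one comparison stated for aim 2 can show an association between texting and outcome. As written, it cannot support a statement of aTS impact on SVR or questionnaire outcomes. This should be corrected, because nothing else stated in the plan addresses that aim.

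A reader might infer that the results are biased in favour of the aTS by a material amount. The documents do not support that: they give neither the size nor the direction of any prognostic gap, nor the reasons why patients did not authenticate. The fractions above rest on a zero aTS effect, a common patient mix across clinics and assumed counts. A reader might also infer that comparing all seven aTS clinics with the two comparison clinics would give a clean answer. It would not: it is very imprecise, the comparison clinics were chosen purposively, and if decliners are not in the data, aTS-clinic participants are already filtered by interest in texting.

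That text-response adherence cannot be compared between the groups follows directly from its definition.

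**What to change.** 1. Report texters, aTS-clinic non-texters and comparison-clinic patients as three groups. State where decliners and authenticated patients who did not text are counted, and reconcile the two descriptions of the authentication step.
2. Adjust the texter comparisons for the collected baseline covariates (self-rated health, engagement and activation, technology use, demographics, regimen), or use one propensity score if SVR failures are few. Account for clinic: compare with aTS-clinic non-texters within clinic, and with comparison-clinic patients through adjusted clinic means, since clinic terms would absorb that contrast. Report an association, and the number of patients lacking a baseline questionnaire.
3. Report text-response adherence descriptively among texters only. Use questionnaire adherence between groups, and state when aTS-clinic non-texters completed the follow-up, which is timed by weeks of aTS use.
4. Optionally, show the seven aTS clinics against the two comparison clinics as a complementary analysis with clinic-level small-sample inference. State the imprecision and both sources of confounding given above.

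Items 1 to 3 are re-analysis and re-labelling of data described as collected. Item 4 would need data on decliners to avoid the filter on interest. The costs are smaller groups, wider intervals, loss of patients without a baseline questionnaire from the full adjustment, and a more cautious conclusion. Confounding by unmeasured factors remains.

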### **Data Analysis**

Descriptive and bivariate analyses of facilitation log data were conducted to compare facilitation dose, comparing UI and AI implementation groups. Descriptive and bivariate analyses were conducted on provider and patient questionnaires, text message frequencies, and clinical data to assess differences between implementation groups (UI and AI) in implementation outcomes. We then compared clinical effectiveness outcomes between texters and non-texters. We examined patient progression through the aTS initiation process, by calculating the percent retained from one step to the next, by UI and AI implementation group. Chi-square tests were used to assess differences between the two groups. All analyses were conducted in RStudio Version 1.0.153 and statistical significance was defined as  $p < 0.05$ .xxi

Qualitative interviews were audio recorded, transcribed verbatim, and then analyzed using NVivo 11 software.xxii Thematic analysis of all qualitative data (interview transcripts, meeting notes, text messages) was conducted.xxiii PRISM domains provided the deductive *a priori* codes and other codes emerged with inductive coding. The triangulation of quantitative and qualitative data served as a final step of analysis.

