## **Setting & Participants**

The group of clinics selected reflects a purposive sample based on several criteria, including clinic size and complexity, and geography. HCV clinics were recruited via a national HCV provider email listserv and monthly HCV provider phone call. The seven HCV clinics selected were randomly assigned to either UI or AI, using set randomization, which, with small sample sizes, helps to achieve balance on a set of relevant characteristics – in this case, urban/suburban setting and on HCV patient volume.iv Two additional comparison clinics were selected purposively because they had similar patient volume, clinic complexity, and geographic locale to the other participating clinics.v Thus in total, data were collected from nine VA clinics: four AI clinics, three UI clinics, and two comparison clinics. Care teams within the HCV clinics had different compositions and involved pharmacists, nurse practitioners, registered nurses, and social worker to varying degrees.

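### The UI versus AI questionnaire comparison describes no baseline adjustment and does not say whether follow-up or change scores are compared

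*Combined protocol and SAP*

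**What the plan says.** The Measures and Data Collection section gives two time points for patients: "Patients at each clinic completed baseline and follow-up (after 8-12 weeks of using the aTS) questionnaires". For staff it adds: "Provider questionnaires followed the same schedule". The Data Analysis section then states: "Descriptive and bivariate analyses were conducted on provider and patient questionnaires, text message frequencies, and clinical data", with the purpose "to assess differences between implementation groups (UI and AI) in implementation outcomes". The only test it names is chi-square, placed directly after the analysis of the steps for starting a patient on the automated texting system (aTS). No regression, covariate, repeated-measures model or change score appears anywhere in the document.

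Under Setting & Participants: "The seven HCV clinics selected were randomly assigned to either UI or AI, using set randomization". The result was four AI and three UI clinics, balanced on setting and patient volume.

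Two statements leave the scope open. Data Analysis lists questionnaires among the data compared between UI and AI but names no scale. Measures and Data Collection uses the implementation-outcome label for one item only: "Implementation Outcomes: Texting Use (Intervention)". Some questionnaire topics also concern the aTS itself, listed as "experiences with the aTS (usability, usefulness, working alliance)".

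**The concern.** A bivariate analysis relates two variables, here group and score, so it has no place for a baseline covariate. The baseline score was nevertheless collected. With seven randomised clinics, chance differences in baseline scores such as readiness, activation or self-rated health are plausible, and balancing on setting and volume need not prevent them.

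The two unadjusted options treat such a difference in opposite ways. A follow-up comparison carries part of it forward. A change-score comparison over-corrects and moves the estimate the other way. Because the plan does not say which was used, a reader cannot tell what a reported UI versus AI difference means, or whether the version was chosen after the data were seen. Precision is also at stake, and seven clinics leave little to spare.

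**Working it through.** **Inputs from the document.** Four AI and three UI clinics (Setting & Participants); significance at p < 0.05 (Data Analysis; taken as two-sided). The plan gives no sample size, effect size or SD, so there is no figure of its own to reproduce.

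**Assumed inputs.** ICC 0.05 or 0.10; respondents per clinic m = 5, 10 or 20; r = 0.3, 0.5 or 0.7. Scores are in SD units with equal SDs at both times. Steps 1 to 4 take r as the same within and between clinics; step 5 drops this.

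**Step 1: size of a chance imbalance.** The SD of the AI minus UI difference in baseline clinic means is √[(1/4 + 1/3) × (ICC + (1 − ICC)/m)]. At ICC 0.05 and m = 20 this is √(0.5833 × 0.0975) = 0.238. At m = 10 it is 0.291 and at m = 5 it is 0.374. These hold for simple randomisation; the balancing that was used may lower them.

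**Step 2: what a realised imbalance D does.** The follow-up estimate moves by r × D, the change-score estimate by (r − 1) × D, and the adjusted estimate by 0. The standard errors relative to follow-up-only are √[2(1 − r)] for change and √(1 − r²) for adjusted. With D = 0.24, about one SD of chance imbalance:

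| r | Follow-up shift | Change shift | Adjusted SE / follow-up SE | Adjusted SE / change SE |
|---|---|---|---|---|
| 0.3 | +0.07 | −0.17 | 0.95 | 0.81 |
| 0.5 | +0.12 | −0.12 | 0.87 | 0.87 |
| 0.7 | +0.17 | −0.07 | 0.71 | 0.92 |

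The last column is √[(1 + r)/2].

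**Step 3: interval width.** The t multiplier on 5 df is 2.571. At ICC 0.05 and r = 0.5 the follow-up-only half-width is 2.571 × 0.374 = 0.96 (m = 5), 2.571 × 0.291 = 0.75 (m = 10) and 2.571 × 0.238 = 0.61 (m = 20). The simulated adjusted SDs, which include error in the slope, are 0.332, 0.252 and 0.207, giving 0.85, 0.65 and 0.53.

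**Step 4: does the unnamed choice matter?** In simulation, with t-tests on seven clinic means and no true effect, each version rejects about 5% of the time, but follow-up and change tests give different verdicts in 8% to 9% of trials. With a true difference of 0.5 SD (ICC 0.05, m = 20) they differ in 32%, 35% or 43% at r = 0.3, 0.5 or 0.7.

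**Step 5: if the clinic-level correlation is 0.** Keep individual r = 0.5 and m = 20. The covariance of baseline and follow-up clinic means is then only 0.5 × (1 − ICC)/m.

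- At ICC 0.05 it is 0.02375, so the follow-up estimate moves by 0.02375/0.0975 = +0.24 per unit of imbalance and the adjusted estimate by 0.24 − 0.5 = −0.26. The imbalance is not removed; it returns with the opposite sign. The two SDs are about equal (0.238 adjusted, 0.237 follow-up-only).
- At ICC 0.10 the variance term is 0.145 and the covariance 0.0225. Follow-up-only SD is √(0.5833 × 0.145) = 0.291. Adjusted SD is √[0.5833 × (0.145 + 0.25 × 0.145 − 2 × 0.5 × 0.0225)] = 0.304. Simulation gives about 0.295 and 0.307. This is a small loss.
- In the other direction, clinic-level r of 0.8 at ICC 0.05 gives 0.184 adjusted against 0.238.

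**Step 6: if respondents are pooled.** A t-test that ignores clinic understates the variance by the design effect 1 + (m − 1) × ICC, and rejects with probability about 2[1 − Φ(1.96/√design effect)] when there is no effect. At m = 20 this gives 16% for ICC 0.05 (design effect 1.95) and 25% for ICC 0.10 (design effect 2.9). Simulation gives about 16% and 26%.

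**The case against.** The strongest reply has four parts.

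- **The text is a short summary.** A reader might infer that adjustment is ruled out. The document does not say so; it describes none. That narrower statement stands.
- **The scales are not named.** The topics closest to implementation are aTS usability and usefulness, which have no score before use. Technology experience or quality improvement culture may be context and not outcomes. This limits the point to whichever scales were compared between UI and AI and are meaningful before aTS use. It does not remove it, because Data Analysis expressly lists questionnaires in that comparison.
- **Randomisation already protects the comparison.** A reader might infer that the unadjusted comparison is biased. Over repeated randomisation it is not, provided that enrolment and follow-up response do not depend on UI or AI. That condition is not shown: "To be eligible for the texting protocol, patients had to be starting HCV medication treatment", the offer came from clinic staff, and follow-up came after weeks of aTS use. If it fails, baseline adjustment does not repair it.
- **Clustering is the larger issue, and the gain is modest.** Both are fair. The 5% error rate in step 4 belongs to clinic-level tests and must not be read as a property of the plan, which names no such test. The gain depends on a clinic-level correlation that nobody can read from the document.

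The project ended in February 2018, so new wording cannot serve as pre-specification.

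**Conclusion.** The point holds in a limited form. Baseline scores were collected, no adjustment for them is described, and the compared quantity is not stated. For the scales in scope, either unadjusted version leaves r or (r − 1) times a realised baseline difference in the estimate and usually costs some precision. With r equal within and between clinics, the standard error would fall by about 5%, 13% or 29% against follow-up-only at r = 0.3, 0.5 or 0.7.

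All sizes rest on assumed ICC, m and r. The documents do not support reading adjustment as a guaranteed improvement: with clinic-level r near 0 the gain is nil or slightly negative and the imbalance remains. No primary outcome is named, so the effect is on how secondary questionnaire results can be read, not on a declared main result. The change is worth making because it is cheap and closes an open analytic choice, but only together with inference at clinic level.

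**What to change.** 1. Name the scales compared between UI and AI, and say for each whether it is meaningful before aTS use. Keep aTS usability and usefulness descriptive.
2. For each remaining scale, estimate the UI versus AI difference in follow-up score adjusted for the same scale's baseline score, with inference at clinic level. One way: regress individual follow-up on baseline scores with clinic indicators, form the seven baseline-adjusted clinic means, and compare four with three by a t-test on 5 df.
3. Report the adjusted difference with its 95% CI.
4. State whether baseline scores were taken before or after clinic allocation. If after, say that adjustment does not remove differences in who enrolled or who responded.
5. Label the analysis post hoc if it is chosen after results were seen.

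The cost is revised SAP wording and one regression per scale, with no new data. Respondents without a baseline score are lost. Intervals stay wide: at ICC 0.05, m = 20 and r = 0.5 the half-width is still 0.53 SD. With few respondents per clinic, as is likely for providers, the slope is less well estimated and the gain is smaller.

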## **Design**

This was a multi-site, mixed-methods, randomized, two-group hybrid type 2 study design comparing the effectiveness of usual implementation (UI) and augmented implementation (AI).ii Matched comparison (i.e., no intervention) sites helped to determine effectiveness of the aTS in aiding HCV treatment. The study was reviewed by the Institutional Review Board (IRB) at the Edith Nourse Rogers Memorial Veterans Hospital in Bedford, Massachusetts and determined to be a quality improvement study (VA Handbook 1058.05).iii The project was conducted from February 2017 through February 2018.

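### The UI versus AI cascade starts at the provider's offer and has no eligible-patient denominator, so its step tests cannot show an effect on offering and can tie while reach differs

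*Combined protocol and SAP*

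**What the plan says.** All references are to the combined protocol and SAP.

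- **Randomised contrast.** Setting & Participants: "The seven HCV clinics selected were randomly assigned to either UI or AI, using set randomization". The result was four AI and three UI clinics. The allocation aimed at balance on urban/suburban setting and HCV patient volume.
- **Aim.** The first aim in the Objective is to "qualitatively and quantitatively assess implementation outcomes for the aTS".
- **Steps.** Measures and Data Collection (Texting Use) lists four: the provider's verbal offer, registration in the portal, authentication by replying to the first text, and active texting.
- **Log.** "Providers logged the number of patients who were offered the aTS and noted whether patients enrolled or declined", with reasons for declining. Patients who were never offered the system are not mentioned.
- **Eligibility.** "To be eligible for the texting protocol, patients had to be starting HCV medication treatment". This criterion is not used as a denominator anywhere, and no count of such patients is given.
- **Analysis.** "We examined patient progression through the aTS initiation process", it says, "by calculating the percent retained from one step to the next, by UI and AI implementation group", with chi-square tests between the two groups. Data Analysis also plans general UI versus AI comparisons of questionnaires, text message frequencies and clinical data. It does not name an offer rate or a reach proportion among them.

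**The concern.** The offer is made by clinic staff after their clinic has been assigned. What AI adds is directed at those staff: a toolkit, support for a local champion and outreach initiated by the facilitator. Facilitation in both arms was meant to support adoption. Offering is thus a plausible place for AI to act, and it is the one link for which no rate is specified.

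Patients who were offered the system are a group selected after randomisation. Comparing what they did next describes where patients drop out, but it is no longer a comparison of the randomised arms as a whole. A tie at each step could be reported as no difference between implementation strategies even if one arm brought the system to a much larger share of its patients.

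The interviews do not fill the gap. Patient interviews covered people who used the system or were invited to. Provider interviews may bring up non-offering but cannot give a rate.

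**Working it through.** The plan states no sample size, rate or power for the cascade, so there is no figure of its own to reproduce.

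**1. What can be tested.** Four steps give three proportions: registered/offered, authenticated/registered and active/authenticated. All three are conditional on an offer. Offered/eligible is absent.

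**2. Can the tests tie while reach differs?** All counts are assumed. Take 200 eligible patients per arm and the same retention in both arms (80%, 75%, 90%).

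- UI: 50 offered, then 40, 30, 27.
- AI: 100 offered, then 80, 60, 54.

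Each of the three step tests gives p = 1.00 (Pearson chi-square, no continuity correction). The offer rate is 50/200 = 25% versus 100/200 = 50%. Actively texting per eligible patient is 27/200 = 13.5% versus 54/200 = 27.0%.

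**3. Size over a range.** Authenticated per starter = offer rate × conversion from offer to authentication. If conversion is the same in both arms, gap = (AI offer rate − UI offer rate) × conversion. All inputs are assumed.

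Offers to 90% (AI) versus 50% (UI), varying conversion:

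- 20%: 0.40 × 0.20 = 8 points
- 55%: 0.40 × 0.55 = 22 points
- 80%: 0.40 × 0.80 = 32 points

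Conversion 55%, AI offers to 90%, varying the UI offer rate:

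- 50%: 49.5% − 27.5% = 22.0 points
- 65%: 49.5% − 35.8% = 13.8 points (unrounded 13.75)
- 80%: 49.5% − 44.0% = 5.5 points
- 90%: 0 points

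**4. Starters who cannot be reached by text.** If the share is the same in both arms, the 22.0-point gap shrinks: at 10% it is 0.90 × 22.0 = 19.8, and at 30% it is 0.70 × 22.0 = 15.4. If the share is 30% in one arm and 10% in the other, with offers to 70% of the rest and 55% conversion in both, reach is 0.70 × 0.70 × 0.55 = 27.0% versus 0.90 × 0.70 × 0.55 = 34.7%. That is a 7.7-point gap with no difference in offering or conversion.

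**5. Precision of a clinic-level estimate.** Variance per clinic = p(1−p)[1/m + ICC(1−1/m)], with m starters per clinic. SE = √(var_AI/4 + var_UI/3). Degrees of freedom = 4 + 3 − 2 = 5, and t(0.975) = 2.571. For example, with m = 60, ICC = 0.02 and 49.5% versus 27.5%, the bracket is 0.0363, SE is 0.0684 and the half-width is 17.6 points.

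Half-widths in points (m and ICC assumed):

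| m, ICC | 22.0-point gap | 13.8-point gap | 5.5-point gap |
|---|---|---|---|
| 60, 0.02 | 17.6 | 18.3 | 18.6 |
| 30, 0.05 | 26.4 | 27.4 | 27.9 |
| 15, 0.10 | 36.9 | 38.3 | 39.1 |

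Only the first cell excludes zero: 22.0 ± 17.6 is 4.4 to 39.6.

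**The case against.** **The data are not blind to offering.** The number offered was logged, and allocation aimed to balance HCV patient volume. With similar volumes, a large difference in offering would be visible in the raw counts even if the percentages tied. This stands as a mitigation. But seven clinics split 4:3, with no stated volumes, do not give an equal or known number of eligible patients, so the counts are not rates.

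**Offering may be covered by the general analyses.** The log sits under implementation outcomes, and UI versus AI comparisons of implementation outcomes are planned. However, the data sources listed for those comparisons do not include the offer log, and no rate is named. What follows is that an offer rate was not specified, not that offering went unreported.

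**The cascade does what it says.** This is correct. It is valid as a description of progression, and reach is not named as an estimand. A reader might infer that the cascade is an error; the documents do not support that. What is missing is a companion measure.

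**The replacement is weak.** Eight of the nine illustrative intervals include zero, and unequal reachability by text can create a gap. Treatment starters are also identified after assignment, so the measure needs the assumption that arm did not change who started treatment. All of this stands. It limits how the estimate should be read, but does not make the step tests informative about offering.

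A reader might also infer that AI did increase offering, or that the cascade could favour the wrong arm. The documents contain no offer rates and no sign of selective offering. A reversal would need strongly selective offering in one arm and is not claimed.

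**Conclusion.** The concern holds as a gap in specification. The planned UI versus AI comparison of initiation is conditional on an offer made after randomisation, so it cannot show an AI effect on offering and can show a tie while reach differs. This follows from the definitions of the steps and of the analysis and needs no assumed figures.

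Size and direction are unknown. The 8, 22 and 32 points rest on assumed offer rates of 90% and 50%, equal conversion in both arms and an AI advantage chosen for illustration. If offer rates were equal, nothing is hidden. This is a cheap improvement worth making, not a fault that invalidates the cascade.

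**What to change.** - **Denominator.** Count patients starting HCV medication at each of the seven randomised clinics over the dates of the offer log. The National HCV Dashboard and Corporate Data Warehouse, already used for clinical data, may supply this. Two points need confirming: that they list all starters by clinic and date, and the log dates, which the document does not give.
- **Report.** Give offered, authenticated and actively texting per starter, by clinic and arm, beside the raw offer counts.
- **Reach estimate.** Use authenticated per starter, because authentication is what separates texters from non-texters in the questionnaire section. Note that the Texting Use section lists a fourth step after it. Give the difference in mean clinic proportions (4 AI versus 3 UI) with a 95% t interval on 5 degrees of freedom, presented as an estimate and not a decisive test.
- **Assumption.** State that arm is taken not to have changed who started treatment, and report starters per clinic by arm so that readers can examine this.
- **Cascade.** Keep step-to-step retention as description, and say that it compares groups selected after randomisation.
- **Fallback.** If starter counts cannot be obtained, state that the step tests do not assess offering or reach.

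The cost is one data pull and some wording. Reported percentages will be lower. Some starters may not be reachable by text, and unequal shares could create a gap, so report that share if it was recorded. Intervals will be wide, with half-widths of about 18 to 39 points under the assumed inputs. On timing, "The project was conducted from February 2017 through February 2018" and the text is in the past tense, so the measure would probably have to be labelled post hoc.
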